A critical question from our previous study is whether the positive functional results achieved with a progressive rehabilitation program (i-STRONGER) are negated by sedentary behavior. This will be the first study 1) develop a collaborative, patient-centered model to increase mobility in the SNF setting, 2) apply concepts of behavior change to promote functional recovery after hospitalization by reducing sedentary time and 3) combine a mobility program with a progressive, intensive rehabilitation protocol (i-STRONGER). The results of this study will inform large multi-site trials and provide a clinical framework to promote optimal functional recovery and discharge to the community for older adults following hospitalization.

III. Preliminary Studies/Progress Report:

Our research group analyzed activity monitoring data from similar patients just days before SNF discharge indicated patients took an average of 1,844 steps per day and were sedentary for 83% of the day. To put this finding into context: patients in the SNF were lower than the ~2,500 steps per day considered basal activity (i.e., baseline activity needed for an individual to perform activities of daily living at rest) and ~70% more sedentary than community-dwelling older adults.²⁸ This study demonstrates that there exists a great opportunity for improvement in mobility in this setting.

Our previous efforts to address functional recovery in the SNF using high-intensity, functional resistance training rehabilitation (i-STRONGER), demonstrated superior outcomes including improvements in physical function and gait speed, and cost-effective reductions in length of stay compared to usual care (COMIRB Protocol #: 14-2388 manuscript in preparation). However, during a typical SNF stay, patients receive rehabilitation for 1-2 hours a day and remain sedentary for up to 14 waking hours, which is not reflective of mobility levels needed to thrive in the community.¹⁻³ **A critical question from the previous study is whether the positive functional results with i-STRONGER**

are negated by sedentary behavior. The purpose of this study is to determine if an interprofessional mobility program (HeRo) has a synergistic effect with i-STRONGER in improving patient outcomes.

IV. Research Methods

A. Outcome Measure(s):

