Outcomes data will only be collected on patients who fit the inclusion criteria: adults 18 through 120 years of age who are admitted to a skilled nursing facility, receive at least physical therapy and were ambulatory prior to hospitalization Exclusion criteria: Patients with neurological disorders, such as a acute stroke or acute traumatic brain injury, will be excluded as the best practice for managing these patients is based on motor-control theory versus the progressive strengthening and aerobic approach. Patients on hospice care will be excluded as hospice care is focused on palliative needs and not rehabilitation. Other patients to be excluded will include those with conditions where strength training is contraindicated (as indicated by the American College of Sports Medicine Guidelines for Exercise Testing and Prescription): recent unstable fractures, advanced congestive heart failure (ejection fraction <30%), bone metastasis sites, tumors in strengthening target areas, acute illness, recent myocardial infarction (within 3-6 weeks), weight bearing restrictions on graft or fracture sites, exposed tendon or muscle, absence of pedal pulses, presence of a fistula, and platelet levels <50,000/ μ L.

C. Study Design and Research Methods

This study is a preliminary investigation using a three-stage, pre-post training designs in one SNF (Figure 1). Stage 1 (usual care) and Stage 2 (i-STRONGER) have already been completed (manuscript in preparation; COMIRB #14-2388). Given that the average length of stay in a SNF is 21 days, the pre/post design will consist of three independent samples of patients to include only those that were admitted and discharged within a discrete period. During the 2 year Stage 3 (HeRo) period we will implement the interprofessional mobility program.

[figure not shown]

Figure 1. Study design

Consenting

Patients will provide written informed consent prior to participating in the study. Potentially eligible patients will be identified upon admission by PTs, OTs, SLPs, PTAs, and COTAs at the research site who have a treating relationship with the potential participant. The clinicians will describe the study to potential participants. If the patient is interested, they will sign a HIPAA A form. Following this, a professional research assistant (PRA) or [name] will screen the patient for eligibility and will approach the patient for consenting within the first 4 days of admission to the SNF.

Intervention:

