There is no expectation that the mobility program will cause serious cardiovascular responses or will increase risk of falls. Gardner et al⁴⁸ reviewed controlled clinical trials with exercise interventions for older adults at-risk for falling. No cardiac events or falls were reported in the 12 clinical trials reviewed. A similar mobility program implemented in the acute care setting demonstrated that the group that received the intervention had fewer falls than the control group.²⁷

E. Potential Scientific Problems:

Missing Data. All patients with outcome measurements will be included in the intent-to-treat analysis. Although we will encourage patients to be fully compliant to their assigned treatment regimen, they will not be dropped from follow-up measurements for lack of compliance. Although statistical methods can be used to “adjust” for missing data, these methods rely on the untestable assumption that data are “missing at random” so that the effect of the missingness can be removed through statistical modeling. We will instead focus on preventing missed follow-up visits and evaluate missingness to determine whether the data are consistent with the hypothesis of missing at random or missing completely at random.

Patient population: The SNF population is highly heterogeneous and often demonstrates fluctuations in medical status and is at risk for rehospitalizations. This heterogeneity will lead to variability in data, which will try to address by controlling for variables such as gender, age, and comorbidities.

F. Data Analysis Plan:

Aim 1 analysis: The proportion of patients in the HeRo group with a score of $\geq 70\%$ on the satisfaction survey will be compared to the null value of 75% using a one sample binomial proportions test. In addition, treatment fidelity checklist scores will be compared to the null value of 90% using a one sample binomial proportions test. For the qualitative component, verbatim transcripts will be independently coded by two study team members. Themes will be developed from those codes as an iterative process until consensus is reached among team members.

Aim 2 primary analysis: The primary analysis will be an intent-to-treat comparison of the differences among treatment groups in change in gait speed at time of SNF discharge. Statistical inference regarding the difference between treatment groups will be based on the estimated coefficient for a treatment group indicator variable in a linear regression

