model with change in gait speed as the response variable, and explanatory variables that include an indicator of treatment group and the baseline value of gait speed. The baseline gait speed value is included to improve the precision/power of the inference about treatment differences. The conclusion about the statistical significance of differences between groups will be determined by this single statistical test to protect against an elevated risk of false-positive conclusions. Sensitivity analysis will be done to evaluate whether conclusions would differ when other important covariates are added to the model (age, gender, comorbidities). We will model gait speed change as a function of treatment group (categorical Stages 1, 2 and 3), controlling for the baseline value of function, study stage, sex, age, length of stay, total therapy minutes, and potential confounders.

Aim 2 Secondary Analysis: Differences between groups in SPPB, falls, successful discharge to the community at time of discharge from SNF will be analyzed as described above. Secondary analyses will be evaluated for their consistency with the conclusions of the primary endpoints. We anticipate that group differences in secondary measures will be correlated with the primary so that significant differences in the primary endpoint will be reinforced by similar effects on secondary endpoints. This approach will reduce the risk of false-positive conclusions resulting from multiple statistical tests.

Sample Size Estimates

Statistical power was estimated based on measurements of gait speed change from admission to discharge on patients in both Stage 1 and Stage 2 (data collection complete, N=80). For the primary outcome (change in gait speed), we used the standard deviation of 0.28. A sample size of 155 patients (75 in Stage 3 [i.e HeRo]) will provide 80% power to detect a clinically meaningful difference in change of 0.16 m/sec between Stages 1 & 3 (primary analysis). In our previous research, 2/3rds of patients met the inclusion criteria at any given time. With an average length of stay of 21-25 days in SNFs, we should have no difficulty enrolling 75 patients for this study.

G. Summarize Knowledge to be Gained:

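### The test that decides Aim 2 names only baseline gait speed as an adjuster in a historical comparison, and a second, unlabelled model repeats stage and adjusts for post-admission variables

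*Combined protocol and SAP*

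**What the plan says.** The design section (IV.C) describes "three independent samples of patients to include only those that were admitted and discharged within a discrete period". Stages 1 and 2 are complete, and the HeRo patients of Stage 3 are compared with them as historical controls at one facility.

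The Aim 2 primary analysis (IV.F) regresses change in gait speed on variables that include a treatment group indicator and baseline gait speed. The reason given for the baseline term is precision: "The baseline gait speed value is included to improve the precision/power of the inference about treatment differences". The decision rule follows: "The conclusion about the statistical significance of differences between groups will be determined by this single statistical test". Age, gender and comorbidities come next, with a different role: "Sensitivity analysis will be done to evaluate whether conclusions would differ when other important covariates are added to the model (age, gender, comorbidities").

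The paragraph then closes with another model, in which gait speed change depends on "treatment group (categorical Stages 1, 2 and 3), controlling for the baseline value of function, study stage, sex, age, length of stay, total therapy minutes", ending in an open-ended reference to potential confounders. The plan does not say whether this model is primary, sensitivity or supportive.

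Two other places bear on this. Section IV.E says of the mixed SNF population: "This heterogeneity will lead to variability in data, which will try to address by controlling for variables such as gender, age, and comorbidities". Section III reports that the earlier i-STRONGER programme produced "cost-effective reductions in length of stay compared to usual care".

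**The concern.** In a randomised trial, a baseline-only model would be an ordinary choice, because allocation balances the other prognostic factors on average. Here nothing balances them. Patients admitted in different periods can differ in age, comorbidity or reason for admission, and any such difference that baseline gait speed does not capture goes straight into the stage coefficient. The plan recognises the heterogeneity and names variables to control for it, but leaves those variables out of the named adjusters for the one test that settles significance.

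The second model would adjust for more, but it cannot serve as the remedy as written. Its role is undefined, its covariate list is open, one term is redundant, and two of its adjusters are measured after treatment starts. Two analysts following the same paragraph could present different treatment effects as the Aim 2 result.

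**Working it through.** **The plan's own figure.** Inputs from Sample Size Estimates (IV.F): SD 0.28, difference 0.16 m/s, 75 in Stage 3, 80 in Stages 1 and 2 combined, 80% power for Stage 1 versus Stage 3. The split of the 80, the alpha and the sidedness are not given; I assume two-sided 5%.

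SE = 0.28 × √(1/n₁ + 1/75), and normal-approximation power follows from 0.16/SE:

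| Stage 1 n | Power |
|---|---|
| 30 | 75.3% |
| 36 | 80.5% |
| 40 | 83.1% |
| 50 | 87.9% |

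The stated 80% is plausible for a Stage 1 n in the mid-30s, but cannot be confirmed without the split. The concern does not depend on it.

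**Case-mix bias in the deciding test.** Suppose HeRo has no effect, but a between-stage difference b remains after adjusting for baseline gait speed. The test rejects with the probability that a noncentral t with noncentrality b/SE exceeds the two-sided 5% limits. Residual df are 155 − 4 = 151 (intercept, two stage indicators, baseline). The SD is kept at 0.28.

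| Assumed b (m/s) | n₁ = 30 (SE 0.0605) | n₁ = 40 (SE 0.0548) | n₁ = 50 (SE 0.0511) |
|---|---|---|---|
| 0.03 | 7.8% | 8.5% | 9.0% |
| 0.05 | 13.0% | 14.8% | 16.3% |
| 0.08 | 26.0% | 30.5% | 34.3% |

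For scale, take one omitted covariate with an assumed partial correlation of 0.3 with gait speed change and an assumed shift of 0.5 SD between stages. The bias is 0.3 × 0.5 × 0.28 = 0.042 m/s, which is 0.042/0.16 = 26% of the target difference. With 40 in Stage 1 the error rate is 11.9%. All these biases are hypothetical.

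**The duplicated stage term.** On an assumed 40/40/75 layout, the second model without the extra term has an intercept, two stage indicators, baseline, age, sex, length of stay and therapy minutes: 8 columns, rank 8. Adding *study stage* as a number gives 9 columns; as a category, 10. The rank stays 8 both times, so no separate stage effect can be estimated.

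**The two lists side by side.** The sensitivity sentence names age, gender and comorbidities. The second model names sex and age, does not name comorbidities, and adds study stage, length of stay and therapy minutes. It is therefore not simply the sensitivity analysis restated.

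**Post-admission adjusters.** Length of stay and total therapy minutes are known only once the stay is under way. Section III reports that i-STRONGER shortened stay against usual care. Stage 3 continues i-STRONGER (IV.C), and the powered contrast is Stage 3 against Stage 1, so length of stay may lie on the path from treatment to outcome. Holding it fixed estimates something other than the total effect. The documents support neither a size nor a direction for the change, and I give none.

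**The case against.** The plan does state a decision rule: significance comes from one test, placed directly after the model with group and baseline gait speed. On that reading the significance decision is not ambiguous, and the longer model merely spells out the fuller adjustment. The wording of the primary model also leaves room for more covariates. Baseline gait speed is the baseline of the outcome itself and removes some imbalance whatever the reason given for including it. All stages come from one facility, and the study calls itself preliminary. Length of stay is each patient's exposure time between the two measurements, which is a recognisable reason to adjust for it. The earlier evidence on stay concerns i-STRONGER, not HeRo's added effect, and nothing in the documents shows that therapy minutes respond to treatment. Finally, the bias values are assumed, and 0.08 m/s is half the target difference.

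Much of this is fair. The decision rule does point to the baseline-only model, the duplicate term is an editorial matter, and the error rates are illustrations. But if the rule holds, the sensitivity analysis cannot alter the conclusion, and the plan gives no rule for disagreement between the two. If the covariate list is open, the deciding test is not fully pre-specified. The second model has no label, and its list does not match the sensitivity sentence. Exposure time is a reason to keep a length-of-stay model as a labelled exploratory analysis, not to leave it without a role under the primary heading.

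**Conclusion.** The concern holds and should be fixed. On the text alone, the deciding test in a non-randomised historical comparison names one adjuster, while the covariates the plan says it will control for have no part in the decision. A second model under the same heading has no role, an open list, a stage term that cannot be estimated separately, and two post-admission adjusters that change the estimand.

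The practical size is unknown, because the documents give no case-mix data by stage. Assuming 30 to 50 patients in Stage 1, SD 0.28 and a two-sided 5% test, residual biases of 0.03 to 0.08 m/s would put the false-positive rate between about 8% and 34%. That range shows how sensitive the test is; it does not estimate the bias in this study.

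**What to change.** - **Name one primary model:** change in gait speed on three-level stage, baseline gait speed, age, sex and comorbidities, with Stage 3 versus Stage 1 as the contrast, as already powered.
- **Fix the covariates and their coding** before Stage 3 outcomes are analysed. Add other pre-treatment variables listed in IV.A, such as primary diagnosis, prior level of function and hospital length of stay, only if they are confirmed as recorded in all three stages.
- **Keep the baseline-only model** as a sensitivity analysis.
- **Delete** *study stage* as a covariate, and replace the closing phrase of "length of stay, total therapy minutes, and potential confounders" with the fixed list.
- **Report SNF length of stay and total therapy minutes** descriptively by stage, or in an exploratory analysis labelled as such with its estimand stated.
- **State the limitation** that stage is also calendar period, so period effects remain under any covariate list.

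The cost is SAP wording and a check of what the Stage 1 and 2 dataset (COMIRB 14-2388) holds, comorbidities included. Age, sex and a one-term comorbidity score lower the residual df from 151 to 155 − 7 = 148. By the noncentral t with an assumed 40 versus 75, power at 0.16 m/s stays at about 82.6%. If the added covariates explain an assumed 5% or 10% of the variance of the stage contrast, its variance rises by 1/0.95 = 1.053 or 1/0.90 = 1.111, and power falls to about 80.7% or 78.5%, before any gain in precision from the covariates. Diagnosis terms with several categories would cost more.

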Title: Patient-Centered, Interprofessional Approach to Improve Functional Outcomes in a Skilled Nursing Facility

NCT04300413

Version Date: 01.28.2020

IRB Approval Date: 03.04.2020

COMIRB Protocol
COLORADO MULTIPLE INSTITUTIONAL REVIEW BOARD
[name] [contact] [contact]

Protocol #: 19-2490

Project Title: Patient-Centered, Interprofessional Approach to Improve Functional Outcomes in a Skilled Nursing Facility

Principal Investigator: [name], MPT, PhD

Version Date: 01.28.2020

I. Hypotheses and Specific Aims:

For many older adults, a skilled nursing facility (SNF) stay is required to address functional deficits stemming from hospitalization. However, during a typical SNF stay, patients receive rehabilitation for 1-2 hours of their day and remain sedentary for up to 14 waking hours, which is not reflective of the mobility levels needed to thrive in the community.¹⁻³ While a previous high-intensity strengthening intervention implemented by our group (COMIRB Protocol #: 14-2388, Intensive Therapeutic Rehabilitation for Older Skilled Nursing Home Residents: i-STRONGER) demonstrated superior outcomes when compared to usual care, the benefits of rehabilitation are likely negated by sedentary behavior outside of structured rehabilitation time. We propose that an interprofessional movement program combined with i-STRONGER strengthening will be feasible, acceptable, and will lead to superior patient outcomes.

AIM 1: Determine the feasibility and acceptability of implementing a structured mobility program High-Intensity Rehabilitation plus Mobility (HeRo) for SNF residents and staff

H1: HeRo will be acceptable to SNF residents: SNF residents will score $\geq 70\%$ in the patient satisfaction survey and will indicate acceptability in semi-structured interviews. HeRo will also be feasible, as evidenced by $>90\%$ treatment fidelity scores by providers.

AIM 2: Determine the effectiveness of HeRo for improving patients' gait speed, short physical performance battery (SPPB), and physical activity levels (i.e. upright time, steps per day) compared to a) the usual care group and b) the i-STRONGER only group.

H2: Patients who participate in HeRo will demonstrate greater gains in gait speed, SPPB, and physical activity over the course of a SNF stay when compared to the usual care group and the i-STRONGER only group.

II. Background and Significance:

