Intervention *Mobility program*

Participants in the study will participate in a regular, structured mobility program outside of rehabilitation time, guided by a mobility coach (a licensed certified nursing assistant [CNA] or physical therapist assistant [PTA]). In current SNF clinical practice, CNAs and PTAs regularly perform walking and other physical activities with patients, so this does not provide any additional risk to the participant. The CNA or PTA will be an employee of the University and a study team member included on the Personnel Form. A Professional Services Agreement between the University and the Veterans Community Living Center at Fitzsimmons will ensure adequate liability coverage, and will outline the services that the mobility coach will provide to the facility. In addition, the mobility coach will obtain Workers without Compensation (WOC) status through the Veteran's administration prior to providing the intervention.

During the first three days of the skilled nursing facility stay, the patient will wear an activity monitor (the Accusplit) to establish baseline level of mobility (i.e. steps per day) in the intervention in order to set and monitor goals, and provide patient feedback. The Accusplit is an inexpensive, non-invasive activity monitor that has been shown to have the best accuracy of commercially-availability activity monitors for older adults with slow gait speed.⁴⁵ Concurrently, patients will wear an ActivPAL device to monitor activity levels as an outcome for the study. Participants will not receive feedback directly from the ActivPAL, but it will be used for data collection as it is a more reliable and detailed measure of physical activity than the Accusplit.

Following the baseline period, the patient will select two goals: a daily step count goal/range for the remainder of the week, between 33-55% increase in step counts as well as a functional goal related to mobility and participation in life roles and activities (i.e. walking to the activity room or dining room twice per day, walking outdoors) or a goal related to time spent out of bed. Patients will keep a diary of activities performed outside of bed, which the mobility coach will review with the patient daily.²⁷ Patients will sign a pre-commitment contract in order to enhance accountability for reaching goals.

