Following the baseline assessment period, participants will start out their week with 70 points. If the participant does not reach one of their two goals, then they will lose 10 points for that day. If they do reach their goal, they will remain at 70 points. If either of the two goals are unable to be assessed, then the patient will keep the 10 points. This method is used to leverage loss aversion, the idea that humans are more prone to change behavior if they fear losing as opposed to gaining a desired outcome.⁴⁶

At the end of each week, the participant will choose a prize with levels depending on how many points he or she have remaining. Prizes may include mugs, medals, calendars, photo frames, jigsaw puzzles, tote bags, crafts, fanny packs, scarfs, and stress balls. These prizes will be provided by the University of Colorado and given by a professional research assistant. If the individual is admitted and discharges within one week, they will receive a prize if they reach goals for half of their days while admitted.

The intervention will also include training for staff on improving mobility. PTs, OT, COTAs, and/or PTAs will provide verbal presentations and demonstrations for nursing staff on safe patient handling techniques as well as a description of the mobility intervention and eligibility for the study.

Progressive rehabilitation

The Veterans Community Living Center at Fitzsimons is already implementing a progressive rehabilitation strengthening program (i-STRONGER) as a result of our previous work with the facility. In brief, i-STRONGER is a standardized, progressive, multi-component program consisting of strengthening, activities of daily living training, and motor control training. The therapists in this facility adopted i-STRONGER as a new standard of care and continue to implement the intervention. Therapists will continue to utilize i-STRONGER as their standard of care throughout the intervention period.

Treatment fidelity

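### Aim 2 compares HeRo with both usual care and i-STRONGER alone, but one test decides the primary analysis and only Stage 1 versus Stage 3 has a power figure

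*Combined protocol and SAP*

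**What the plan says.** **What is to be shown.** Section I, Aim 2, lists two comparators, and H2 predicts greater gains "when compared to the usual care group and the i-STRONGER only group". Section III adds: "The purpose of this study is to determine if an interprofessional mobility program (HeRo) has a synergistic effect with i-STRONGER in improving patient outcomes". Section IV.C (Comparison groups) promises comparison with both historical groups.

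**How the stages relate.** Section IV.C says "the pre/post design will consist of three independent samples of patients to include only those that were admitted and discharged within a discrete period". i-STRONGER is not withdrawn in Stage 3: "Therapists will continue to utilize i-STRONGER as their standard of care throughout the intervention period". Section III reports that i-STRONGER "demonstrated superior outcomes including improvements in physical function and gait speed, and cost-effective reductions in length of stay compared to usual care".

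**How the decision is made.** Section IV.F (Aim 2 primary analysis) describes a comparison among the groups. Inference rests on the coefficient of one treatment indicator in a regression of gait-speed change, with baseline gait speed as the other term. That one test settles significance, to limit false positives. The paragraph ends with a further model that has stage in three categories and also controls for study stage, among other variables.

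**Power.** Section IV.F (Sample Size Estimates) uses an SD of 0.28, 80 patients in Stages 1 and 2 together and 75 in Stage 3, and says that this "will provide 80% power to detect a clinically meaningful difference in change of 0.16 m/sec between Stages 1 & 3 (primary analysis"). The documents do not give the Stage 1/Stage 2 split, the alpha level or sidedness, the size of the i-STRONGER effect, or an expected difference between Stages 3 and 2.

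**The concern.** H2 has two comparators, and a single coefficient can address only one contrast. The label in the sample-size paragraph points to usual care versus HeRo. That contrast combines whatever i-STRONGER already achieved with whatever HeRo adds. The question in the stated purpose, whether HeRo adds to i-STRONGER, depends on Stage 3 versus 2. That contrast has no role in the decision and no power figure.

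At stake is the reading of a positive result. A significant Stage 1 versus 3 test could be taken as support for HeRo when it reflects i-STRONGER alone. It could then be carried into the cluster-randomised trial that Section IV.G says this study should inform.

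**Working it through.** **Inputs from Section IV.F:** SD 0.28, difference 0.16 m/s, 75 in Stage 3, 80 in Stages 1 and 2 together.

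**Assumptions:** 40 in Stage 1 and 40 in Stage 2 (brackets give the range over splits of 30/50 to 50/30), two-sided 5%, no period difference, no dropout, no baseline adjustment unless stated.

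**1. The plan's own figure.** SE = 0.28 × √(1/n₁ + 1/75). With n₁ = 40, SE = 0.0548 and 0.16/0.0548 = 2.92. The noncentral t on 113 df gives 82.5% power (normal approximation 83.1%). Exactly 80% needs about 35 in Stage 1 by the normal approximation; 37 gives 80.5% by t. The stated 80% is therefore plausible for Stage 1 versus 3. Pooling all 80 earlier patients against 75 would give 94% (97% at one-sided 5%), so the figure does not describe a pooled comparison.

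**2. HeRo adds nothing.** The Stage 1 versus 3 difference is then the i-STRONGER effect, and the Stage 3 versus 2 difference is zero. The two contrasts share Stage 3, so their correlation is (1/75)/(1/40 + 1/75) = 0.348.

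| i-STRONGER effect (m/s) | Stage 1 vs 3 significant | Both contrasts significant in HeRo's favour |
|---|---|---|
| 0.08 | 30% (26–34) | 1.6% |
| 0.10 | 44% (37–49) | 1.9% |
| 0.16 | 82% (75–87) | 2.4% |

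**3. An omnibus reading.** With mean changes of 0, 0.16 and 0.16 above usual care in Stages 1, 2 and 3, the F test on 2 and 152 df rejects 79% of the time, although HeRo adds nothing. It does not show superiority over each comparator either.

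**4. Power for Stage 3 versus 2 (75 vs 40).** 82% (75–87) for an increment of 0.16, 58% (50–64) for 0.12, and 30% (26–34) for 0.08.

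**5. Joint power for the gait-speed part of H2.** Both contrasts must be significant. Figures come from 1,000,000 simulated three-group trials with pooled SD; the bivariate normal agrees within about 1 point.

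| i-STRONGER effect | HeRo increment | Gap 3 vs 1 | Joint power |
|---|---|---|---|
| 0.08 | 0.16 | 0.24 | 82% (75–86) |
| 0 | 0.16 | 0.16 | 71% (68 at 30/50 or 50/30) |
| 0.08 | 0.08 | 0.16 | 28% (25–30) |

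If baseline gait speed correlates 0.4 with change (an assumption), the SD becomes 0.28 × √0.84 = 0.257. The three joint figures become about 88%, 80% and 34%.

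**6. The three-category model.** An intercept (1), stage as a factor (2), baseline (1) and study stage again as a factor (2) make 6 columns of rank 4. Stage effects are not separately identified as written. Deleting the duplicate term restores them.

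**The case against.** Several points on the other side are fair.

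- **The contrast is not named.** The primary-analysis text speaks of differences among groups. A reader might infer that the plan fixes Stage 1 versus 3 as the deciding test. The documents only point that way, through the label in the sample-size paragraph. This limits the wording of the concern but does not remove it: no single coefficient covers both comparators, and the omnibus reading fails as well.
- **Stage 3 versus 2 is not absent.** Section IV.C commits to it, and the three-category model could estimate it. The repeated stage term is most likely a drafting slip. What is missing is a deciding role and a power statement.
- **The 30%, 44% and 82% are not false-positive rates.** In those scenarios Stages 1 and 3 truly differ, so rejection is correct for that contrast. The figures mislead only if read as support for HeRo over i-STRONGER, and the plan nowhere says that Stage 1 versus 3 alone establishes that.
- **Power may be adequate.** Scenarios that hold the total gap at 0.16 look poor, but one of them makes i-STRONGER worth nothing, against Section III. With 0.08 from i-STRONGER and 0.16 from HeRo, joint power is 82%.
- **The study is described as preliminary.** That would justify calling Stage 3 versus 2 exploratory. The plan does not do so; it states a directional hypothesis against both groups and a significance rule.

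**Conclusion.** The concern holds: the stated rule does not answer the two-comparator hypothesis. A significant Stage 1 versus 3 result would support i-STRONGER plus HeRo over usual care, and nothing more specific. If HeRo adds nothing, that result still occurs 30% to 82% of the time for i-STRONGER effects of 0.08 to 0.16 m/s, against about 2% when both contrasts are required.

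Two stronger readings are not supported. A reader might infer that the 80% is wrong; it is plausible for Stage 1 versus 3. A reader might also infer that the study is underpowered for H2. Joint power for gait speed ranges from 28% to 82% across the effects tried and is near target when the increment is 0.16. The documents give neither the increment nor the i-STRONGER effect, so the shortfall is possible but not shown.

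All sizes rest on the assumed split, increments and two-sided 5%, and on no period difference between non-randomised stages. They concern gait speed only, whereas H2 also covers SPPB and physical activity. Adjustment for length of stay and therapy minutes is a separate question and is not needed for this conclusion.

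**What to change.** 1. In the baseline-adjusted primary model, enter stage once as a three-level factor and delete the duplicate study-stage term.
2. Replace the single test with two named contrasts, Stage 3 versus 1 and Stage 3 versus 2, each at two-sided 5%. Claim the gait-speed component of H2 only if both are significant. This needs no alpha split. If Stage 3 versus 1 is also to be claimed alone, specify a fixed testing order.
3. State that Stage 3 versus 1 alone supports only the combined package over usual care.
4. State that the 80% applies to Stage 3 versus 1 only. Add Stage 3 versus 2 power and joint power, using the actual Stage 1 and Stage 2 sizes and a stated increment.
5. Always report the Stage 3 versus 2 estimate with its 95% CI, and note that it may also reflect period differences between non-randomised stages.

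Alternatively, label Stage 3 versus 2 exploratory and reword H2 and the stated purpose to match.

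**Cost:** protocol wording and a recalculated power statement, with no extra patients. The downside is that stated power for the two-comparator claim may fall below 80%, depending on the assumed increment. With 40 in Stage 2, the 95% CI for Stage 3 versus 2 would be about ±0.11 m/s (1.98 × 0.0548).
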